14.3 Recording and Follow up of Adverse Events

Up to Day 85 (Visit 10), the subjects will be instructed to spontaneously report all AEs to the site staff or Investigator as soon as possible. Any AEs observed or reported by a subject and/or staff up to Day 85 (Visit 10) will also be recorded in the eCRF. The Investigator will review results from the physical examinations. All new and aggravated findings, as compared with baseline, must be identified and recorded as AEs in the eCRF. Following Day 85 (Visit 10) AEs will be recorded by the subject in a diary card, and only relevant or significant AEs will be recorded in the eCRF.

AEs already recorded and designated as 'continuing' should be reviewed at each subsequent assessment.

For all AEs, the Investigator must obtain adequate information to determine the outcome of the AE and to assess whether it meets the criteria for classification as an SAE. For all AEs, sufficient information should be obtained by the Investigator to determine the causality of the AE (i.e. study vaccine or other illness). The Investigator is required to assess causality and record that assessment on the eCRF. Follow-up of the AE, after the date of therapy discontinuation, is required if the AE or its sequelae persist. Any AE that is still ongoing at the post-study medical visit will have an outcome of 'ongoing' recorded in the eCRF, however the Investigator will continue to follow up ongoing related AEs and record information in the source documents. Related SAEs will be followed until the event resolves or the event or sequelae stabilise and this information will be reported to the Sponsor using the SAE reporting forms.

14.4 Serious Adverse Events and Suspected Unexpected Serious Adverse Reactions (SUSARs)

A SAE is any AE that:

- results in death
- is life-threatening
- requires inpatient hospitalization or prolongation of existing hospitalization
- results in persistent or significant disability or incapacity
- consists of a congenital anomaly or birth defect.

Important medical events that may not be immediately life-threatening or result in death or hospitalization but may jeopardise the patient or may require intervention to prevent one of the other outcomes listed in the definition above should also be considered serious.

A SUSAR is an adverse reaction, which is both serious and unexpected.

I4.5 Reporting Timelines

I4.5.1 SAE Reporting

An SAE must be reported immediately (within 24 hours), independent of the circumstances or suspected cause, if it occurs or comes to the attention of the Investigator at any time during the study period. Any SAE with a suspected causal relationship to the IMP occurring at any other time after completion of the study must be promptly reported.

Contact Details for SAE Reporting:

The following mandatory information must be provided to the Sponsor pharmacovigilance contact within 24 hours for each SAE:

- Protocol number
- Subject number
- AE
- IMP
- Investigator's name and contact details

Causality assessment should be completed as soon as possible.

Follow-up information should be actively sought until the SAE has resolved or sequelae have stabilised. Additional information e.g. hospital reports or death certificates, may be requested by the Sponsor and should be anonymised/pseudonymised before transmission and subsequently filed in the Investigator Site File.

The expectedness of an SAE shall be determined by the Sponsor according to the most recent version of the Investigator's Brochure.

I4.5.2 SUSAR Reporting

The Sponsor shall ensure that all relevant information about a suspected unexpected serious adverse reaction (SUSAR), which occurs during the course of a clinical trial in the United Kingdom and is fatal or life-threatening is reported as soon as possible to the MHRA, the competent authorities of any EEA State, other than the United Kingdom, in which the trial is being conducted, and the relevant Ethics Committee. This needs to be done not later than seven days after the sponsor was first aware of the reaction. Any additional relevant information should be sent within eight days of the report.

The Sponsor shall ensure that a SUSAR which is not fatal or life-threatening is reported as soon as possible and in any event not later than 15 days after the Sponsor is first aware of the reaction.

I4.6 Abnormal Findings from Investigations or Assessments

Abnormal findings from investigations or assessments will be recorded as AEs if the Investigator considers they are clinically significant and/or result in medical intervention. This may include but is not limited to abnormal laboratory results, physical examination findings and vital sign

values/changes.

14.7 Pregnancy

Pregnancy is not an adverse event but the outcome of a pregnancy might be an adverse event. Over the course of the 6 month follow up it is possible that one or more subjects may become pregnant after day 85. It is important that any pregnancy is followed up. On being notified of a pregnancy the Investigator will complete a pregnancy notification form, which will be submitted to [REDACTED], and will inform the Sponsor. [REDACTED] will seek permission to follow up the pregnancy and at the time of the estimated date of delivery will contact the Investigator to remind the Investigator to determine the outcome of the pregnancy with the subject.

15. STATISTICAL EVALUATION

Details of the planned statistical analyses will be described in the Statistical Analysis Plan (SAP) and some important features are presented in this protocol. Statistical analyses will be performed by ████████ using SAS version 9.3.

15.1 Statistical method description

15.1.1 General information

Demographic, baseline characteristics and data recorded during the study will be summarized using descriptive statistics by treatment (placebo or vaccine) and dose group, unless otherwise specified.

Individual data will be presented as a data listing, sorted by treatment and administered dose level.

For parameters with evaluation before vaccination and in case of re-checked value(s), only the last observation prior to dosing will be used in descriptive and inferential statistics and derivations of other parameter values. After vaccination, only values of scheduled assessments (planned in the protocol) will be used.

For laboratory/clinical parameters for which laboratory/reference ranges will be available, position of parameter values according to ranges will be flagged with the following rule:

- "L" for values lower than laboratory/reference ranges;
- "H" for values higher than laboratory/reference ranges.

In addition, parameter values can be assessed by investigator and flagged as follows in order to determine clinical relevance:

- Normal;
- Abnormal and NCS (Not clinically Significant);
- Abnormal and CS (Clinically Significant).

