12.3 Safety Assessments

The description of safety assessments is given below, and the timings of these assessments is given in the Schedule of Assessments. The time points of the safety assessments may change depending on information gained throughout the study, however the total number of safety assessments per subject will not be reduced, although unscheduled assessments may be performed at the discretion of the Investigator.

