15.4.2 Primary endpoint

The primary objective is to evaluate the safety and tolerability of the GBS-NN/NN2 vaccine for 12 weeks after the first dose of vaccine.

All the subjects included in the SAF set (including the withdrawal and dropout subjects) will be evaluated for safety analysis.

The following endpoints will be evaluated:

- **Local and systemic reactogenicity**

Assessment results will be described according to treatment/dose group and visit.

- **Adverse events**

Adverse events will be coded according to the Medical Dictionary for Regulatory Activity (MedDRA, latest version). They will be classified into pre-defined standard categories according to chronological criteria:

Treatment Emergent Adverse Events (TEAEs): AEs which occur for the first time after the first administration or present before and worsened during vaccine exposure.

Non-Treatment Emergent Adverse Events (NTEAEs): AEs which occur before the first study vaccine administration (also called “pre-dose event”).

TEAEs will be described by relation to study vaccine (for example: related or unrelated) and maximum intensity (for example: mild / moderate / severe) according to treatment/dose group. Descriptive statistics will be characterised by number of TEAEs, number and percentage of subjects with at least one TEAE (based on SAF). In case of few TEAEs (≤ 5 per study part for example), only a listing will be performed.

If descriptive statistics are performed, vaccine relation of TEAEs (*i.e.* related or not related to study vaccine) will be summarized by MedDRA codes (SOC and PT) and treatment/dose group.

Two distinct listings of TEAEs and NTEAEs will be presented by treatment/dose group, subject and MedDRA codes in order to provide more information about adverse events (example: description, duration, time since last administration if

applicable, seriousness, relation to study vaccine, any actions taken as concomitant medication or hospitalization).

- **Laboratory tests**

Biochemistry and haematology tests will be performed at V1 (screening), V2, V4, V5, V8, post-study medical V10 and V11.

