Parameter values, position according to laboratory ranges (if available) and investigator assessment will be listed according to visit for each treatment/dose group. In order to assess study evolution of parameters after vaccination, parameter values changes from pre- to post-dose visits (baseline to pre second dose Day 29 (effect of first dose) and baseline and pre second dose to 28 days after second dose (Day 57) then base line to Day 85). will be calculated. Emergent values (for parameters with available laboratory ranges; values not within this range) with their corresponding position according to ranges will be listed by treatment/dose group and subject.

- **Urinalysis**

Urinalysis will be performed at V1 (screening), V4, V8 and post-study medical visit V10.

Parameter values (quantitative or binary results, *i.e.* positive/negative), position according to laboratory ranges (if available) and investigator assessment will be listed according to visit for each treatment/dose group. In order to assess study evolution of continuous parameters after vaccination, parameter values changes from screening to post-study medical visit will be performed. Emergent values (for parameters with available laboratory ranges or with binary results) will be listed by treatment/dose group and subject.

- **Vital signs**

Vitals signs will be characterised by heart rate, blood pressure, oral temperature and respiratory rate. Vital signs will be assessed at V1 (screening), V2 (pre-dose, T2h and T4h post-dose), V3, V4, V5, V6 (pre-dose and T2h post-dose), V7, V8, and post-study medical V10 and V11.

Parameter values, position according to reference ranges (if available) and investigator assessment will be described according to visit and assessment time for each treatment/dose group. In order to assess study evolution of parameters after vaccination, parameter values changes from pre-dose to post-dose assessments will be performed. Emergent values (for parameters with available reference ranges; values not within this range) with their corresponding position according to reference ranges will be listed by treatment/dose group and subject.

- **12-lead ECG parameters**

ECGs will be assessed at V1 (screening).

Parameter values, position according to reference ranges and investigator assessment (if available) will be described according to visit for each treatment/dose group. Emergent values (for parameters with available reference ranges; values not

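### The scheduled-only rule for post-vaccination values has no safety exception, so unscheduled out-of-range and peak values can drop out of the parameter summaries and, read literally, the emergent-value outputs

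*Combined protocol and SAP*

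**What the plan says.** Section 15.1.1 first deals with pre-dose re-checks, where "only the last observation prior to dosing will be used in descriptive and inferential statistics and derivations of other parameter values". The next sentence is the rule at issue: "After vaccination, only values of scheduled assessments (planned in the protocol) will be used". It names no particular output and makes no exception for safety data. The synopsis repeats both sentences.

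Section 12.3 foresees results outside the schedule: "unscheduled assessments may be performed at the discretion of the Investigator". Section 12.2 (Visits 2 and 6) adds oral temperatures that subjects take at home if they feel unwell in the week after each dose. Table 1 in Section 18 has no row for these.

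Section 15.4.2, within the primary endpoint, lists laboratory and urinalysis values by visit and describes vital signs by visit and assessment time. Local and systemic reactogenicity is also described by visit. For laboratory tests, urinalysis and vital signs it adds a listing of out-of-range results; the laboratory wording is "Emergent values (for parameters with available laboratory ranges; values not within this range". It does not say whether an unscheduled result can qualify, and it describes no worst-value or any-time summary.

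**The concern.** Using only scheduled values is sound for by-visit means. It gives each subject one value per time point and stops frequently measured subjects from carrying extra weight. Finding abnormal values is a different task. A result obtained between visits is likely to have been sought because of a symptom or a worry, so a rule that discards it tends to make the parameter-level results look cleaner than the data.

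The primary objective is safety and tolerability to Day 85, and there are only 24 vaccinees per dose. A reader of the report would take the emergent-value listings as the record of which subjects went out of range after vaccination. If unscheduled results are absent from them, that record is incomplete and nothing in the output would show it.

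**Working it through.** The plan gives no figure on this point to reproduce, so the check is a comparison of sections, with one labelled illustration.

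**1. How far the rule reaches.** Taken alone, the sentence covers any use of post-vaccination values. Read with the sentence before it, it covers descriptive statistics, inferential statistics and derived values. Parameter summaries fall under it on either reading. Emergent status is found by comparing a value with a range, so it can be treated as a derivation, but the output is a listing and listings are not named. Its exclusion is therefore the literal reading rather than a settled one.

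**2. Where results can only be unscheduled.** Nominal post-dose days up to Day 85, from Table 1 and Sections 12.2 and 15.4.2:

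| Assessment | After dose 1 (Day 1) | After dose 2 (Day 29) |
|---|---|---|
| Safety laboratory | Days 8, 15 | Days 43, 85 |
| Urinalysis | Day 8 | Days 43, 85 |
| Vital signs | Days 1, 2, 8, 15, 29 (pre-dose 2) | Days 29, 30, 43, 85 |
| Injection site | Days 1, 2, 8, 15, 29 | Days 29, 30, 43, 57, 85 |

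- First scheduled laboratory test after dosing: 8 − 1 = 7 days after dose 1; 43 − 29 = 14 days after dose 2.
- Gap in vital signs and injection-site checks after the 24-hour visit: 8 − 2 = 6 days after dose 1; 43 − 30 = 13 days after dose 2.
- The home-temperature week after dose 2 ends on Day 29 + 7 = 36. The only scheduled temperatures inside it are those on Days 29 and 30.

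A laboratory result, or an injection-site measurement at the clinic, on Day 33 would thus be unscheduled by construction. Home temperatures are less clear. The protocol plans for them, but they are triggered by symptoms and have no fixed time, so they are probably excluded rather than certainly.

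**3. What the adverse event route recovers.** Section 14.6: "Abnormal findings from investigations or assessments will be recorded as AEs if the Investigator considers they are clinically significant and/or result in medical intervention". Section 14.1 also counts as an adverse event a deterioration in a laboratory or clinical measurement that leads to symptoms, changed treatment or discontinuation. Section 14.3: "Any AEs observed or reported by a subject and/or staff up to Day 85 (Visit 10) will also be recorded in the eCRF". Section 15.4.2 reports the "number and percentage of subjects with at least one TEAE (based on SAF"). None of these depends on the visit schedule.

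**4. What is left.** Two things are not recovered:
- unscheduled out-of-range values that cause no symptoms, are not treated and are judged not clinically significant, a category that Section 15.1.1 itself defines for flagging;
- the size of a peak, because the adverse event tables give intensity and relation to vaccine, not the measurement.

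**5. Scale (illustration only).** The documents give no count of unscheduled abnormal values, so the number of affected subjects in one dose arm of 24 is assumed:
- 1 subject: 1/24 = 4.2%
- 2 subjects: 2/24 = 8.3%
- 3 subjects: 3/24 = 12.5%

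If one such subject were the only case, leaving her out would change 1/24 (exact two-sided 95% interval 0.1% to 21.1%) to 0/24 (0% to 14.2%, the upper limit being 1 − 0.025^(1/24) = 0.142). The plan produces no such proportion or interval. The figures show only what one subject weighs in an arm of this size.

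**The case against.** A reader might infer that the rule removes unscheduled results from the primary safety analysis. The documents do not support that. Adverse events are part of the primary endpoint and are collected whatever their timing, so most of what prompts an unscheduled test is captured. The safety committee's review (Section 12.5) and the stopping criteria (Sections 12.6 and 12.7) are not limited to scheduled values. Section 15.1.1 also promises, without restriction, that "Individual data will be presented as a data listing, sorted by treatment and administered dose level". All of this stands, and it confines the point to parameter-level outputs.

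A reader might also infer a demonstrated bias of known size, or a distortion between arms. Neither is shown. Some unscheduled results are repeats of an abnormal scheduled value that has already been counted. The trial is double-blind, and nothing in the documents shows that unscheduled testing would differ by arm. The direction, towards understating abnormality, is a reasonable expectation; the amount is unknown.

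Finally, Section 15 leaves analysis detail to the SAP, so this could be called detail still to come. That answer is weaker. The protocol states a rule rather than leaving a gap, and no SAP text in the document supplied modifies it.

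**Conclusion.** The point holds for parameter summaries and derivations and, on a literal reading, for the emergent-value outputs. The loss is limited to out-of-range values judged not clinically significant and not acted on, and to the size of peaks between visits. The schedule leaves most room for this in the two weeks after dose 2. The effect tends to understate abnormality and cannot be quantified from the documents.

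The conclusion rests on three assumptions: that unscheduled assessments do take place, that they are more often prompted by concern than by routine, and that the rule is programmed as written. It does not call into question adverse event reporting, dose-escalation review or the stopping criteria. It is a modest defect, worth correcting because the correction is specific and cheap.

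**What to change.** In Section 15.1.1, the synopsis and the SAP, limit the scheduled-only rule to by-visit summaries and changes from baseline. In Sections 15.1.1 and 15.4.2, state that emergent-value listings, and any worst post-dose value per subject, use all recorded post-dose results, scheduled and unscheduled, including home temperatures, with unscheduled results marked as such.

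The cost is small: some extra programming, and uneven numbers of measurements per subject in those outputs, which a footnote can explain. No visit or sample is added. The sponsor should first confirm that unscheduled results and home temperatures are entered in the eCRF in a form that can be analysed, since the protocol does not say so.

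The same edit should reconcile a related inconsistency. Section 15.4.2 plans laboratory changes to Day 29 and Day 57, but neither that section nor Table 1 schedules laboratory tests at Visit 6 or Visit 9. Under a scheduled-only rule those changes cannot be calculated.

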15.1.2 Descriptive statistics

Descriptive statistics for quantitative parameters will be provided using number of observations (N), Geometric mean, 95% confidence intervals, standard deviation (SD), minimum, median and maximum. Descriptive statistics for qualitative parameters will be provided using absolute frequencies (n) and relative frequencies (%). For immunological endpoints (IgG concentration and fold increase) geometric means with 95% confidence intervals for the geometric mean will additionally be presented.

15.1.3 Inferential statistics

Statistical tests will be carried out to compare results between treatment groups, depending on studied variable type. These analyses will be fully detailed in the SAP.

For categorical endpoints, such as local and systemic reactogenicity, a comparison of events intensity (scores) between groups can be performed with an adequate statistical test dealing with categorical variables (for example: Fisher exact test, Chi square test or generalized estimating equations).

For continuous endpoints, such as immune response induced by different GBS-NN/NN2 vaccine dosing regimens, appropriate statistical methods (for example: ANOVA or ANCOVA) can be used to compare pre-vaccination and post-vaccination levels as well as post-vaccination levels between groups.

15.2 Studied populations for each study part

The following populations will be taken into account for each study part:

- **Randomized Set (RAN):** All included subjects who are randomized at V2 to one of the two cohorts;
- **Safety Set (SAF):** All subjects from the SAF set who receive at least one dose of the study vaccine (or placebo) will be taken into account in the description of the population (demographic or baseline characteristics);
- **Immunogenicity Set (IG):** The subset of subjects from the SAF set who will receive at least one dose of the study vaccine (or placebo) with available pre- and post-vaccination titres.
- **Per Protocol Set (PP):** All subjects from the IG set who receive both doses of the study vaccine (or placebo) and provide evaluable samples for analysis of the IgG antibody response to the GBS-NN/NN2 vaccine at Day 85 (most important immunological endpoint) and do not violate the protocol.

The safety analyses will be performed on the SAF set. The immunological analyses will be performed on the IG set. The most important immunological endpoint (immune response on Day 85) will also be performed on the PP set if the number of subjects in the PP set differs by more than 5% from the number of subjects in the IG set.

Missing or incomplete data will not be replaced, unless otherwise specified (example: values strictly under the LLOQ for immunogenicity data).

